### 7.3.2 Secondary analyses

Secondary analyses are planned for occurrence of post-thrombotic syndrome (PTS), number of dabigatran etexilate dose adjustments (i.e. Number of patients with dabigatran dose adjustments) and pharmacodynamic assessments at Visit 3 (after at least six consecutive dabigatran etexilate doses) and after at least 3 days following any dabigatran etexilate dose adjustment.

- Occurrence of PTS will be summarized by K-M estimate of time to first occurrence. The K-M rate and descriptive rate at 6 and 12 month will be calculated. Early drop out, lost-to-follow-up and death will be considered as non-event and censored.
- Frequency of dabigatran etexilate dose adjustments will be summarized descriptively. This refers to the number of patients with dabigatran etexilate dose adjustment during treatment period because each patient is allowed to have only one dose adjustment.
- pharmacodynamic analyses details can be found in [Section 7.3.5](#) and [7.3.6](#).

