**FLOW CHART**

Trial Period	Screening	Treatment Period (open-label) with Dabigatran Etexilte											Follow-up		
Visit (V) #:	1 	2 	3 	4	5	6	7	8	9	10	11	Titration Visit (if needed) 	Unscheduled Visit (if needed) 	eEOT   If medication is discontinued before Visit 11	12
Study week	-1	1	1	3	6	12	18	26	34	42	52				V11 or eEOT + 28 days +7
Day visit window	-14 to 1	1	4 +3	22 ±7	43 ±7	85 ±7	127 ±7	183 ±7	239 ±7	295 ±7	365 ±7				
Informed consent / assent 	X														
Inclusion / exclusion criteria	X	X													
Medical history / demographics	X														
Physical examination 	X							X			X			X	X
Assessment of Index VTE and clinical risk factor	X														
Vital signs (BP and HR) and weight	X	X	X	X	X	X	X	X	X	X	X	X	X	X	X
Height	X							X			X			X	
12-lead resting-ECG (5 min supine) 	X							X			X			X	
Evaluate signs / symptoms of recurrent VTE and clinical risk factor		X	X	X	X	X	X	X	X	X	X	X	X	X	X
Evaluation of PTS								X			X				
Evaluation of bleeding events		X	X	X	X	X	X	X	X	X	X	X	X	X	X
Objective diagnosis of recurrent VTE or bleeding		In case of suspected recurrent VTE, PTS or bleeding													
Pregnancy test 	X							X			X			X	
Laboratory tests (blood) 	X	X	X	X	X	X	X	X	X	X	X	X	X	X	X
PD sample (aPTT and ECT) 		X	X	X	X	X	X	X	X	X	X	X		X	
dTT (or alternative method) sample 			X	X	X	X	X	X	X	X	X	X		X	
First administration of dabigatran etexilate 		X													
Dispense dabigatran etexilate		X	X	X	X	X	X	X	X	X			X		
Adverse events and Concomitant Therapy	X	X	X	X	X	X	X	X	X	X	X	X	X	X	X
Medication compliance			X	X	X	X	X	X	X	X	X	X	X	X	
Patient treatment assessment 			X	X		X		X			X			X	
Investigator treatment evaluation			X	X		X		X			X			X	
Termination of trial medication											X			X	
Conclusion of Patient Participation															X

Proprietary confidential information.

© 2019 Boehringer Ingelheim International GmbH or one or more of its affiliated companies. All rights reserved.

This document may not - in full or in part - be passed on, reproduced, published or otherwise used without prior written permission.

1. Screening Visit and Visit 8 of 1160.106 trial may be combined for patients who have completed the treatment period of 1160.106 trial (tests will be done only once)

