2. Visit 1 and Visit 2 may occur on the same day provided that results of the local lab are available to confirm eligibility and INR is  $\leq 2.3$  (for patients who have been treated with VKA). Local lab results will be recorded under Visit 1, central lab results will be recorded under Visit 2 in the eCRF.
3. Visit 3 is not applicable for patients who have previously completed the treatment period in the dabigatran etexilate arm of the 1160.106 study and who continue taking the same dose of dabigatran etexilate in this trial. For all other patients, during Visit 3 the trough dabigatran concentration will be determined

The first concentration assessment will be done at Visit 3 (after at least 6 consecutive dabigatran etexilate doses are taken). If target trough exposure of 50 to  $< 250$  ng/mL is not achieved, an Unscheduled Visit must be performed in order to adjust the dabigatran etexilate dose (refer to [Appendix 10.4.2](#)). A Titration Visit must be scheduled preferably after at least 3 days have elapsed (or at least 6 new doses have been taken) since a dose adjustment to reassess if the new trough dabigatran concentration is within the target range. Trough is achieved 10 to 16 hours after the last intake of dabigatran etexilate. Patients must not be dosed at home prior to attending a Titration Visit; dosing will be done after a trough plasma sample is collected.

4. Unscheduled Visits are to be conducted in all cases of suspected recurrent VTE, paradoxical embolism (PDE), occurrence of post-thrombotic syndrome (PTS), major or clinically-relevant bleeding events (MBEs/CRBEs) or other AESI or SAE. The Unscheduled Visit should be performed as soon as possible, preferably within 24 hours after the site first becomes aware of a suspected event.  
Unscheduled Visit is also to be performed in case a dose adjustment is needed.
5. The early End Of Treatment (eEOT) Visit will be required for all patients who have taken a dose of dabigatran etexilate but the study medication was discontinued early for any reason (e.g. the clinical risk factor has resolved) before Visit 11. For transition recommendation from dabigatran etexilate to a non-study antithrombotic treatment see [Appendix 10.3](#)

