6. The informed consent (and if applicable assent) should be obtained per local legislations and guidelines from the patient's parent(s) or legal guardian and patient (where applicable) before any study procedures are performed. Should patients reach legal age during the trial they must personally sign and date the informed consent form as soon as possible and, at the latest, at the next visit.
7. A complete physical examination is required at Visit 1, Visit 8, Visit 11, eEOT Visit and Visit 12. At any point during the trial, a comprehensive physical examination should be performed if indicated based on the clinical presentation of the patient (reported symptoms and the findings on the basis of the vital signs). Relevant findings should be recorded in source notes and captured in the trial eCRF.
8. The required ECGs should be performed as noted in the [flow chart](#), additional ECGs should be performed in cases of cardiac symptoms (example: rhythm disorders) or per PI judgment when medically required.
9. A pregnancy test will be done centrally in female adolescents of child bearing potential (subjects who have reached menarche). Menstrual period must be confirmed prior to inclusion in the trial. More frequent testing can be done if required by the local regulation and / or authority or per investigator judgment. Alternatively serum or urine pregnancy testing may be performed locally at screening, see protocol [Section 5.2.3](#).
10. Laboratory tests will be performed according to protocol [Section 5.2.3](#).

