##### Secondary endpoints:

- Occurrence of post-thrombotic syndrome (PTS) at 6 and 12 months  
An appropriate instrument (e.g. the Manco-Johnson Instrument or Villalta scale or a similar instrument; the chosen instrument will be available in the ISF)
- Pharmacodynamic assessments (central measurement of dTT (Anti-Factor IIa activity), aPTT and ECT) at Visit 3 (after at least six consecutive dabigatran etexilate doses) and after at least 3 days following any dabigatran etexilate dose adjustment
- Number of dabigatran etexilate dose adjustments during treatment period (i.e. Number of patients with dabigatran dose adjustments during treatment period)

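### PTS is analysed as time to first occurrence, but the PTS evaluation is first scheduled at Visit 8, so PTS unrecognised at entry would count as an on-study event

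*Protocol*

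**What the plan says.** Protocol section 5.2.1 lists occurrence of PTS at 6 and 12 months as a secondary endpoint, to be assessed with a recognised instrument such as the Manco-Johnson or Villalta scale. Section 7.3.2 gives the analysis: "Occurrence of PTS will be summarized by K-M estimate of time to first occurrence", and "The K-M rate and descriptive rate at 6 and 12 month will be calculated". Its only handling rule for PTS is that drop-out, loss to follow-up and death are censored as non-events.

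In the Flow Chart the row "Evaluation of PTS" is marked at Visit 8 and Visit 11 and nowhere else. Two other routes to a PTS finding exist:

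- **At entry.** Visit 1 has medical history and an assessment of the index VTE. Footnote 7 adds: "A complete physical examination is required at Visit 1, Visit 8, Visit 11, eEOT Visit and Visit 12".
- **Between scheduled evaluations.** The objective-diagnosis row applies "In case of suspected recurrent VTE, PTS or bleeding", and footnote 4 and section 6.2.2 call for an Unscheduled Visit when PTS is suspected.

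Under section 3.3.2 every patient has either completed at least 3 months of initial VTE treatment or completed treatment in 1160.106. Neither 3.3.2 nor 3.3.3 mentions PTS. For rollover patients, footnote 1 says that the "Screening Visit and Visit 8 of 1160.106 trial may be combined for patients who have completed the treatment period of 1160.106 trial". It does not say whether a PTS score was taken there.

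**The concern.** A time to first occurrence has a clear meaning only for patients known to be free of the condition at time zero. PTS is a consequence of a VTE, and all patients have had that VTE before time zero. The scheduled evaluation is first made about six months into treatment, so a positive result at Visit 8 can be new PTS or PTS that was there from the start.

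The trial has one arm and reports descriptively, so the absolute rate is the result. No control arm carries the same share of pre-existing cases against which it could be compared. A reader who takes the rate as PTS arising on dabigatran would be reading a mixture of new and carried-over cases in unknown proportion.

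**Working it through.** **Schedule against analysis.** Among the numbered visits, the PTS row has marks at Visit 8 (day 183) and Visit 11 (day 365). It is blank at Visits 1 and 2, at eEOT and at Visit 12. The analysis treats every patient as at risk of a first occurrence. Nothing in the protocol establishes by instrument that a patient is PTS-free at entry.

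**What the documents give on size.** There is no entry prevalence, no expected new rate and no rollover share. Section 1.1 cites background PTS frequencies of 10% (clinically significant PTS), 6.3% (a cohort with median follow-up of 24 months) and 21% (a registry followed for 6 months to 3 years). None of these is a prevalence at entry to this trial.

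**Illustration. All of q, r and s are assumptions.** Let q be the proportion with unrecognised PTS at entry and r the true new 12-month rate among the rest. Assume no drop-out and that every entry case is found by Visit 11.

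Apparent rate = q + (1 − q) × r

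| q | r = 2% | r = 5% |
|---|---|---|
| 0% | 2.0% | 5.0% |
| 2% | 0.02 + 0.98 × 0.02 = 4.0% | 0.02 + 0.98 × 0.05 = 6.9% |
| 5% | 0.05 + 0.95 × 0.02 = 6.9% | 0.05 + 0.95 × 0.05 = 9.8% |
| 10% | 0.10 + 0.90 × 0.02 = 11.8% | 0.10 + 0.90 × 0.05 = 14.5% |

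The last row is an extreme. It sets unrecognised entry PTS equal to the whole 10% background estimate.

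**How far Visit 1 helps.** Now let q be total entry prevalence, and suppose that history and examination recognise a share s of these cases, which are then taken out of the risk set.

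Apparent rate = [q(1 − s) + (1 − q)r] / (1 − qs)

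With q = 5% and r = 2%:

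- s = 0: 0.069 / 1 = 6.9%
- s = 0.5: (0.025 + 0.019) / 0.975 = 4.5%
- s = 0.8: (0.010 + 0.019) / 0.960 = 3.0%
- s = 1: 0.019 / 0.950 = 2.0%

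The bias disappears if Visit 1 recognises every case and those patients are set apart.

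**Precision of a rate among PTS-free patients.** The plan gives no PTS figure of its own, but Table 7.6:1 gives the 95% Wilson interval for 2 events in 100 as 0.55–7.00%. It reproduces: centre (0.02 + 3.84/200) / (1 + 3.84/100) = 3.78%, half-width 3.23%. With the same 2 new cases, the interval is 0.58–7.35% for 2/95 and 0.61–7.74% for 2/90.

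**The case against.** Four arguments on the other side deserve weight.

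1. **The classification rule belongs in the SAP.** This stands. A rule separating PTS at entry from new PTS is commonly left to the SAP, which is not shown, so its absence from 7.3.2 is not an error. A SAP cannot, however, create an entry score that the Flow Chart never collects.

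2. **PTS would be noticed anyway.** Visit 1 includes history, a complete examination and assessment of the index VTE, and later suspicion leads to an Unscheduled Visit. Section 5.2.2.2 also requires an onset date for each adverse event. A reader might infer that the protocol has no means of seeing PTS at entry, and that is not so. What is left is PTS that raises no suspicion before Visit 8. None of these steps is the instrument, so the gap is narrowed and not closed.

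3. **The net direction is uncertain.** This partly stands. Section 6.2.3 lets patients off drug continue by telephone, and eEOT has no PTS evaluation, so some cases may be missed and the rate lowered. That is a separate mechanism. Carried-over PTS acts only upward, but the balance of the two cannot be stated.

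4. **Occurrence at 6 and 12 months may mean presence at those times.** The endpoint wording in 5.2.1 permits this reading, under which the descriptive rate alone would be interpretable. It does not fit a Kaplan–Meier time to first occurrence, which treats every patient as initially event-free.

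**Conclusion.** The point holds for PTS that is present at entry and not recognised at Visit 1 or at an Unscheduled Visit. Such cases would enter the 6- and 12-month rates as on-study occurrences and push them upward. The size cannot be derived. The illustration runs from no bias to an apparent 11.8% for a true 2%, and depends wholly on assumed q, r and s.

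Two stronger readings are tempting and unsupported. One takes the 6.3–21% background figures as entry prevalence and concludes that most reported PTS would be old. Those figures describe other cohorts over follow-up and say nothing about what Visit 1 would miss. The other treats the safety conclusions of the trial as compromised. PTS is one secondary, descriptive endpoint with no hypothesis test, and neither the primary endpoints nor the sample size depends on it.

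Severity: minor; a cheap improvement.

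**What to change.** - **Flow Chart:** add the same PTS instrument at Visit 1 for patients still to be enrolled. For rollover patients, use a score from Visit 8 of 1160.106 if one was recorded.
- **Section 7.3.2:** keep the planned Treated Set rates. Add the number of patients with PTS at entry, and the K-M and descriptive rates among patients free of PTS at entry. Reporting both is sounder than replacing the planned rates, because the PTS-free group would rest on uneven entry information.
- **Patients already enrolled:** classify entry status from the Visit 1 history and examination, and state that this is less sensitive than the instrument.

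The cost is one short clinical scale at a visit that already has a complete examination, and a few sentences of text. The added rate has a slightly smaller denominator, with the small loss of precision shown above. Entry status would come from sources of unequal sensitivity, which should be stated beside the result. The current text is the eighth amendment, so the instrument helps only patients not yet enrolled, a number the protocol does not give.

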### 7.3.3 Safety analyses

The safety analyses will be descriptive in nature and will be based on BI standards. Parameters to be evaluated for safety are described in [Section 5.2](#).

AEs will be coded using the MedDRA dictionary. All AEs will be classified according to the following trial periods: screening, treatment, safety follow-up. All AEs with an onset date / time after administration of trial medication up to 3 days after the last intake of study medication will be assigned to the treatment period for evaluation. In addition, AEs with onset date before start of the trial treatment but with worsening in intensity during the treatment will also be assigned to the on-treatment period. Other AEs will be assigned to the screening or post-treatment period, respectively. All AEs (including bleeding) in the treatment period will be tabulated in total and according to seriousness, severity and possible relationship to trial medication. AEs in the screening or follow-up period will be listed.

### 7.3.6 Pharmacodynamic analyses

The following descriptive statistics will be calculated for the pharmacodynamic parameters aPTT, ECT and any additional PD assay: these include, but are not limited to N, arithmetic mean, standard deviation, minimum, median, and maximum. Further, ratios to baseline (i.e. Visit 2) for these parameters will be calculated and assessed by descriptive statistics.

Dabigatran concentrations derived from dTT or alternative methods, e.g. ecarin based tests, will be compared to dabigatran concentrations determined by HPLC-MS/MS. This comparison will be reported separately.

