**Proprietary confidential information.**

© 2019 Boehringer Ingelheim International GmbH or one or more of its affiliated companies. All rights reserved.

This document may not - in full or in part - be passed on, reproduced, published or otherwise used without prior written permission.

The approximate blood volumes (in ml) to be collected for planned central safety laboratory assessments and /PD are outlined in [Appendix 10.1.1](#). An additional blood sample could be collected at screening for local measurement of INR, serum creatinine, HCT, Hb, Platelet count, ALT and AST in order to facilitate the eligibility assessment.

In case of infants and when medically required per Investigator judgment and / or per local guidelines, reduced blood collection will be implemented after consultation with the Sponsor (e.g. omission of exploratory coagulation markers, reduced frequency of safety labs during the treatment period, etc.). The decision for the reduced blood collection in those cases will be documented in the ISF.

11. Collection of pre-dose trough PD samples will be done as indicated in the [flow chart](#). Pre-dose trough PD samples should be taken at approximately 10 to 16 hours after the last dose. Date and exact time of study drug administration on the three days before the samples are taken are to be captured using patient / parent / legal guardian diary (must be distributed during the previous visit). Dabigatran etexilate doses must not be delayed to accommodate a preferred pre-dose collection time point. More frequent plasma level evaluations may be warranted per investigator judgment for infants and in cases where the patient's weight is expected to fluctuate in a short timeframe due to patient age, physiology and other factors.
12. The appropriate dabigatran etexilate starting dose must be based on the latest age and weight-based nomogram provided in [Appendix 10.4.1](#). Patients who completed the treatment period of the 1160.106 study and who are still being treated with dabigatran etexilate may continue taking the same dose also in this trial.

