### 3. DESCRIPTION OF DESIGN AND TRIAL POPULATION

#### 3.1 OVERALL TRIAL DESIGN AND PLAN

This is a multi-centre, multinational, open-label, single arm prospective cohort study of dabigatran etexilate to evaluate safety in the secondary prevention of venous thromboembolism in children from 0 to less than 18 years. This study is planned to be conducted in approximately 100 sites located worldwide.

After a signed consent form (and assent, if applicable) has been obtained and if all eligibility criteria are met, patients will initiate or continue treatment with dabigatran etexilate (Visit 2). Detailed guidance on how to switch from standard VTE treatment to dabigatran etexilate is provided in [Section 4.1.4](#).

Patients will be treated with dabigatran etexilate until the clinical risk factor requiring secondary VTE prevention has resolved, or up to a maximum of 12 months. The clinical risk factor must be specified at screening and evaluated at every visit. At the end of the study all patients need to discontinue dabigatran etexilate, or switch to standard of care, if there is continued need for anticoagulant treatment (see [Appendix 10.3](#)).

Please refer to [Section 4.1.3](#) for information on dose selection.

Study visits and procedures will be performed as outlined in the [Flow Chart](#). Collection and processing of PD samples is described in [Section 5.7.2](#).

All patients who have taken dabigatran etexilate will have a follow-up period of 28 days after termination of trial medication (Visit 11). Subject participation is concluded when the Follow-up Visit is completed.

Patients who stop study treatment earlier than 12 months (risk factor resolved or early treatment discontinuation) will be asked to perform an eEOT Visit and will be followed up according to the remaining visit schedule until the end of the study. Prior to entering the trial, patients and their parents / legal guardians will be made aware of this requirement.

The end of the trial is defined as “last subject out”, i.e. last visit completed by the last subject.

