### **5.2.3 Assessment of safety laboratory parameters**

A central laboratory will be used for the analysis of all laboratory measurements with the exception of serum or urine pregnancy test, INR, serum creatinine, HCT, Hb, Platelet count, ALT and AST measurement at screening (if applicable) which may be done locally to facilitate the eligibility assessment. If needed and when feasible a local laboratory may alternatively be used for dTT testing to evaluate dabigatran concentration. Local lab assessments are also acceptable in emergency situations (e.g. bleeding event or emergency surgery), see [Appendix 10.1](#).

Refer to the [Flow Chart](#) and [Section 5.7.2](#) for additional information.

For patients who have completed the treatment period of study 1160.106, the lab results from Visit 8 will be taken as Visit 1 or Visit 2 results of this trial, depending on the day Visit 1 and Visit 2 take place in correlation to Visit 8 of study 1160.106 (see [Flow Chart](#), Footnotes 1 and 2).

A centralized serum pregnancy test for females who have reached menarche will be done as noted in the Flow Chart.

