### 7.3 PLANNED ANALYSES

The primary analysis will include patients who were dispensed study medication and have received at least one dose of study medication (Treated set).

The analysis of the /PD parameters will be performed on Pharmacokinetic set (PKS). PKS will include all treated patients with at least one /PD measurement and having no protocol violations relevant to the evaluation of PD endpoints.

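### Section 7.3.6 takes Visit 2 as the aPTT/ECT baseline for everyone, but patients rolling over on dabigatran from 1160.106 are already on drug at Visit 2, so ratios summarised over the whole set understate prolongation

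*Protocol*

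**What the plan says.** Section 7.3.6 plans descriptive statistics for aPTT and ECT and adds that "ratios to baseline (i.e. Visit 2) for these parameters will be calculated and assessed by descriptive statistics". The visible text makes no exception for treatment before entry.

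Other sections show who can be on dabigatran at that visit:

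- Section 3.1: "patients will initiate or continue treatment with dabigatran etexilate (Visit 2"). Continuing is thus foreseen alongside starting.
- Flow Chart footnote 12, on patients who completed the 1160.106 treatment period: those "who are still being treated with dabigatran etexilate may continue taking the same dose also in this trial". Section 4.1.4 repeats this for dose and formulation.
- Section 5.2.3, for patients who completed the 1160.106 treatment period: "the lab results from Visit 8 will be taken as Visit 1 or Visit 2 results of this trial", depending on how the visit days fall. Flow Chart footnote 1 allows the combined visit for patients "who have completed the treatment period of 1160.106 trial (tests will be done only once").
- Flow Chart footnote 3 drops Visit 3 only for patients from the 1160.106 dabigatran arm "who continue taking the same dose of dabigatran etexilate in this trial. For all other patients, during Visit 3" is still done.

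On the analysis set, section 7.3 says "PKS will include all treated patients with at least one" measurement and no protocol violation relevant to the pharmacodynamic endpoints. Section 5.2.1 makes pharmacodynamics a secondary endpoint at Visit 3 "and after at least 3 days following any dabigatran etexilate dose adjustment".

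**The concern.** A ratio to baseline shows how far the drug prolongs clotting only if the denominator was measured without the drug. For a patient starting dabigatran at Visit 2 it was. For a patient continuing from 1160.106 it was not:

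- **Dose unchanged.** The ratio compares one on-drug trough with another and sits near 1 from Visit 4 on, however prolonged the clotting time is.
- **Dose changed.** The ratio shows only the difference between two doses. This includes Visit 3 when the dose changes at entry, and the sample after a later adjustment. If the dose is lowered, the ratio can fall below 1 while clotting is still prolonged.

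A table that summarises both kinds of ratio under one label has no single meaning, and its centre is pulled towards 1. A reader would take the effect of dabigatran on aPTT and ECT to be smaller than it is.

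**Working it through.** **1. Is there an aPTT/ECT sample at Visit 2?** Section 5.7.2 gives a total of about 22.8 mL for pharmacodynamic blood. The Flow Chart and Appendix 10.1.1 show 1.2 mL for aPTT/ECT at Visits 2 to 11 (10 samples) and 1.2 mL for dTT at Visits 3 to 11 (9 samples):

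10 × 1.2 + 9 × 1.2 = 12.0 + 10.8 = 22.8 mL.

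This reproduces the stated figure. Without a Visit 2 sample it would be 9 × 2.4 = 21.6 mL. The baseline value is therefore planned.

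**2. Is that value on drug for a continuing roll-over?** Flow Chart footnote 11 sets trough samples at about 10 to 16 h after the last dose. Section 1.2 gives a half-life of 11–17 h in young volunteers, so the sample falls between 10/17 = 0.6 and 16/11 = 1.5 half-lives after a dose. Section 1.2 also states that aPTT and ECT follow dabigatran concentration, and no washout is described. The value is on drug whether it is a fresh Visit 2 sample or the reused 1160.106 Visit 8 result.

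**3. Effect on the mean, dose unchanged (Visit 4 onwards).** Let p be the share of on-drug roll-overs, R the true ratio to a dabigatran-free value, and r the roll-over's ratio to Visit 2. None of these is in the protocol; all are assumed.

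Mean over the set = (1 − p)R + p·r

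| p | R = 2.0, r = 1 (r = 0.9 to 1.1) | R = 1.5, r = 1 (r = 0.9 to 1.1) |
|---|---|---|
| 10% | 1.90 (1.89–1.91) | 1.45 (1.44–1.46) |
| 25% | 1.75 (1.725–1.775) | 1.375 (1.35–1.40) |
| 50% | 1.50 (1.45–1.55) | 1.25 (1.20–1.30) |

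With r = 1, the fraction of the prolongation lost is [R − (1 − p)R − p]/(R − 1) = p, for any R above 1.

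The median is pulled down too once values vary. In a simulation with assumed log-scale standard deviations of 0.12 (dabigatran-free) and 0.20 (on drug) and R = 2.0, the median ratio was 1.94, 1.82 and 1.46 at p = 10, 25 and 50%.

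**4. Effect for one roll-over whose dose changes.** Section 1.2 describes linear pharmacokinetics and an ECT linear in concentration. For a dose multiple k:

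- ratio to Visit 2 = [1 + k(R − 1)]/R
- ratio to a dabigatran-free value = 1 + k(R − 1)

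| k | R = 2.0: to Visit 2 / dabigatran-free | R = 1.5: to Visit 2 / dabigatran-free |
|---|---|---|
| 0.5 | 0.75 / 1.50 | 0.83 / 1.25 |
| 2 | 1.50 / 3.00 | 1.33 / 2.00 |

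Halving and doubling are the largest steps in Table 4.1.3: 2. The formula does not apply to aPTT, which section 1.2 describes as non-linear.

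**The case against.** - **Pooling is inferred.** Section 7.3.6 fixes a per-patient ratio, not one table over all patients. A SAP could split the table by prior treatment, and parts of the text around sections 7.3 and 7.3.6 are not visible. This is fair, so the conclusion is conditional: any summary over the whole set mixes the two ratios. But the protocol itself names the baseline, and nothing visible re-baselines or separates these patients.
- **No drug-free baseline is promised.** Under section 4.1.4 a patient coming from a vitamin K antagonist may have an INR up to 2.3 at Visit 2, and one on a parenteral agent starts 0–2 hours before the next dose is due. The starters' ratio is therefore not clean either. This stands and limits the claim to a dabigatran-free baseline. It does not make the two kinds of ratio comparable.
- **The secondary endpoint is largely spared.** Same-dose roll-overs have no Visit 3, so the dilution table above describes Visit 4 onwards. At the endpoint time points only roll-overs with a changed dose contribute, and their number is unknown. This stands.
- **The halving example may be rare.** The rationale for amendment 05 reports no trough above range in an interim analysis of 27 patients, and that for amendment 08 reports no excess of high levels below 12 years. This stands: the example shows what the rule can produce, not how often.
- **Little depends on the ratio.** Nothing is tested, section 5.7.1 calls the parameters exploratory, and absolute values are also reported. This bears on severity, not on whether the rule is right.

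**Conclusion.** The concern holds. The Visit 2 rule gives patients continuing dabigatran from 1160.106 a ratio that does not measure prolongation by the drug, and a summary over the whole set is biased towards 1. The direction is certain for any true ratio above 1. The size is not known, because the protocol gives neither the roll-over share nor the true ratio; over the assumed shares of 10 to 50%, with unchanged doses, 10 to 50% of the prolongation in the mean is lost.

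Only roll-overs still on dabigatran are concerned. Patients from the standard-of-care arm of 1160.106 and new patients have a dabigatran-free Visit 2 value. The weight is minor to moderate: it should be corrected, but it affects only the descriptive ratio summaries.

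**What to change.** In section 7.3.6:

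- summarise ratios to Visit 2 only for patients not on dabigatran at Visit 2;
- for patients already on dabigatran at Visit 2, report absolute aPTT and ECT, or a separate ratio table labelled as change from an on-drug value;
- label the main table as relative to a dabigatran-free, not anticoagulant-free, baseline.

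This needs only analysis wording and table labels. It requires no new data and changes no dosing or visit rule. The cost is a smaller main ratio table: 90, 75 or 50 patients per 100 treated at assumed on-drug roll-over shares of 10, 25 or 50%. Any residual effect of a vitamin K antagonist or heparin at Visit 2 remains and is dealt with only by the label.
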